4.7 Rationale for Correlative Science

Novel Models of Metastasis and Circulating Tumor Cell (CTCs). Older models of metastasis portray the unidirectional flow of circulating tumor cells (CTCs) leaving the primary tumor and seeding a metastasis at a distant site (64). However, recent preclinical data using diverse experimental models of breast cancer, colon cancer and melanoma suggest metastasis is a multidirectional process where CTCs seed both distant sites as well as the original primary tumor – a process termed “self-seeding”(65, 66). Proponents of self-seeding have posited that CTC self-seeding of established macroscopic

tumor sites likely requires less or no adaptation of CTCs to the recipient microenvironment in comparison to the colonization of CTCs to a distant and foreign site. In addition, self-seeding CTCs have already undergone selection for movement into and out of the circulation as well as resistance to anoikis. Pre-clinical data have shown that self-seeding CTCs home back and extravasate into the primary in reaction to signals from the recipient primary tumors cells and tumor stroma. These self-seeding CTCs appear to be the most aggressive fraction of the CTC population (65). This feed forward loop of increasingly more aggressive cancer cells interacting with the tumor stroma results in the release of signals that foster tumor growth, angiogenesis, immune evasion, and ultimately macroscopic metastases.

Interestingly, genomic lineage tracing data of metastases from a rapid autopsy series of men who died of metastatic prostate cancer suggest macroscopic metastases represent *communal sanctuaries* that are composed of prostate cancer cells from many other metastatic sites throughout the body of patients (67). These *communal sanctuaries* are favorable niches that allow prostate cancer cells the ability to gain competence for the development of future macroscopic metastases. These human data are consistent with the preclinical concept of “self-seeding” or a multidirectional flow of CTCs. If these provocative data hold true, then SBRT/SABR to all macroscopic metastases in oligometastatic patients may eliminate these *sanctuaries* and alter the natural history of metastatic patients. Following change in CTC numbers and biology following SABR may allow us to interrogate this hypothesis. Interventions that effectively target these macroscopic metastatic sanctuaries, such as SBRT/SABR, in combination with immune mediated therapies appear poised to arrest self-seeding and subsequent maturation of macroscopic metastases.

EPIC High-Definition analysis of single CTCs.

The High Definition-CTC (HD-CTC) method can be used for the longitudinal CTC enumeration and to assess for AR expression (68). The assay employs as little as 1 mL of blood and is an unbiased protocol to distinguish CTCs among the surrounding leukocytes based on their cytokeratin positive (CK+) phenotype by using a high resolution immunofluorescence imaging. All cells are captured, and AR- cells can be evaluated. In addition, the HD-CTC technology preserves the cell morphology in such a way that enables the morphometric and the indirect quantification of AR and CK protein expression levels for all the CTCs identified in the blood sample (Fig. 1). Recently, the HD-CTC method has been used to examine expression of immune checkpoint molecules relevant to our proposal such as programmed cell death-1 (PD-1) on CTCs (data not shown). The HD-CTC assay was technically validated with cell line spiking experiments to reach an $R^2=0.9997$ on linearity testing as previously reported. These experiments were performed using SK-BR-3 cell lines and 0 to 3×10^2 cells per mL of normal donor control blood. The coefficient of variation is 16% and inter-processor correlation is $R^2 = 0.979$. Sample preparation process adhered to standard operating procedures for patient samples through a bar coded system for all consumables and instrumentation. All off-the-shelf instrumentation was calibrated according to analytical validation protocols established during commissioning.

Fig. 1. The HD-CTC assay. Red blood cells are lysed followed by plating of nucleated cells on custom made cell-adhesion glass slides. Slides are stained for cytokeratin (CK), CD45 and DAPI, then CTCs are identified among leukocytes using computerized high resolution immunofluorescence imaging.

[figure not shown]
[figure not shown]

Fig. 2. CAPP-Seq ctDNA detection. (A) Analysis of exome sequencing from many tumors is used to select mutated genomic regions for a custom library of biotinylated oligonucleotides that are used for hybrid capture selection of tumor and germline genomic DNA and ctDNA. (B) Dilution series analysis of expected versus observed frequencies of mutant alleles, assessed by spiking fragmented HCC78 DNA into control cell free DNA.

protocols established during commissioning.

Cancer personalized profiling by deep sequencing (CAPP-Seq) to detect circulating tumor DNA. Circulating tumor DNA (ctDNA) is a promising biomarker for non-invasive assessment of cancer burden, but existing ctDNA

detection methods have either insufficient sensitivity and/or lack broad clinical applicability. [name] laboratory recently published Cancer Personalized Profiling by deep sequencing (CAPP-Seq) (69), an economical and ultrasensitive method for quantifying ctDNA. CAPP-Seq was initially implemented for lung cancer with a design covering multiple classes of somatic alterations that identified mutations in >95% of tumors. We detected ctDNA in 100% of patients with stage II–IV lung cancer and in 50% of patients with stage I, with 96% specificity for mutant allele fractions down to ~0.02%. Levels of ctDNA were highly correlated with tumor volume and distinguished between residual disease and treatment-related imaging changes, and measurement of ctDNA levels allowed for earlier response assessment than radiographic approaches from 1.5 mL of blood (**Fig. 2**). We have designed a prostate cancer-specific CAPP-Seq selector that identifies at least 1 mutation in >95% of prostate tumors with a median of ~4 mutations per tumor. We will apply CAPP-Seq to detect and monitor prostate cancer response to SBRT/SABR.

ImmunoSEQ allows Unprecedented Profiling of the Anti-Tumor Immune Response.

There are now an established body of pre-clinical and emerging clinical literature demonstrating that SABR can profoundly modify anti-tumor immune responses. Radiation induced activation of antigen presenting cells has been demonstrated in animal models to enhance tumor antigen cross-presentation in the draining lymph node and result in activation and proliferation of tumor specific cytotoxic T-cells (78). The cellular adaptive immune system generates a remarkable breadth of diversity in antigen-specific TCRs by combinatorial recombination of gene segments in lymphocytes. The TCR is composed of two peptide chains, encoded by the TCRA and TCRB or TCRG and TCRD genes, respectively. There are thus two types of T-cell receptors, $\alpha\beta$ and $\gamma\delta$, that differ by the TCR heterodimer type and immune function. The antigenic specificity of T-lymphocytes is in large part determined by the amino acid sequence in the hypervariable complementarity-determining region 3 (CDR3) regions of the T-cell receptors. Because of the potential diversity of receptors (a healthy adult has approximately 10 million different TCRB chains contained within their 10^{12} circulating T-cells (70)) it is highly improbable to randomly converge on the same TCRB nucleotide CDR3 sequence, effectively making each CDR3 sequence a unique tag for a T-cell clone. Adaptive Biotechnologies' ImmunoSEQ assay, a multiplex PCR-based method that amplifies rearranged TCR CDR3 sequences and exploits the capacity of high throughout sequencing technology characterizes tens of thousands of TCRB CDR3 chains simultaneously. Thus, the assay captures the full TCR repertoire including specific individual clones. The ImmunoSEQ assay provides a novel method to identify and track the presence and frequency of common and rare clones, in the context of the total adaptive immune system. Recently, ImmunoSEQ showed profound evolution and diversification of the TCR repertoire of men with mCRPC treated with the immune stimulatory agent ipilimumab (71). Improved clinical outcomes were associated with less T-cell clonotype loss, consistent with the maintenance of high-frequency TCR

clonotypes during treatment reported by ImmunoSEQ. These clones may have represented the presence of preexisting high-avidity T cells that may be relevant in the antitumor response.

Rational for Invitae. The evolution of human genome sequencing has enabled the assessment of genetic anomalies in routine clinical practice. According to a recent multicenter study in the *New England Journal of Medicine*, it was reported that inherited mutations in DNA-repair genes were much higher than expected in men with lethal metastatic castrate resistant prostate cancer (79). The study isolated germline DNA of 692 men with metastatic prostate cancer (unselected for family history of cancer or age at diagnosis), and identified 84 deleterious germline DNA-repair gene mutations in 82 of those men (79). This was substantially higher than in men with non-metastatic hormone sensitive localized disease. The prevalence of germline DNA-repair mutations in the oligometastatic hormone sensitive or castrate-resistant state is unknown.

In the Invitae's Multi-Cancer Panel genetic test, Invitae uses a sequencing platform to analyze the risk of developing hereditary cancer due to inheritance of a pathogenic mutation in 84 cancer predisposition genes (81). The Invitae panel, covers 12 of 16 genes (BRCA1, BRCA2, MSH2, MSH6, PMS2, CHECK2, ATM, NBN, BRIP1, RAD51C, and RAD51D) that account for 92% of the germline mutations reported in Pritchard et al NEJM. Thus, inherited prostate cancer genomic data provided by Invitae can further allow investigators to personalize screening and target specified effective therapies for each patient disease (80).

5. PARTICIPANT SELECTION AND ENROLLMENT PROCEDURES

All patients will be eligible to receive systemic therapy alone at the time of clinical or radiographic disease progression.

5.1 Inclusion Criteria

- 5.1.1 Patient must have at least one and up to three asymptomatic metastatic tumor(s) of the bone or soft tissue (with at least one bone metastasis) within the past 3-months that are ≤ 5.0 cm or <250 cm 3 as seen on either CT/MRI scan and/or bone scan. Up to five lesions are allowed on advanced functional imaging such as fluciclovine (Axumin), choline or ^{18}F -DCFPyL (“PyL”) PET-CT scan within the past 6-months. (PET-CT scan is reasonable for study entry imaging as an alternative to CT/MRI scan and/or bone scan)
- 5.1.2 Patient must have had their primary tumor treated with surgery and/or radiation.
- 5.1.3 Histologic confirmation of malignancy (primary or metastatic tumor).
- 5.1.4 PSADT <15 months. PSA doubling time (PSADT) will be calculated using as many PSA values that are available from time of relapse (PSA > 0.2). To calculate PSADT, the Memorial Sloan Kettering Cancer Center Prostate Cancer Prediction Tool will be used. It can be found at the following web site: <https://www.mskcc.org/homograms/prostate/psa-doubling-time>.
- 5.1.5 Patient may have had prior systemic therapy and/or ADT associated with treatment of their primary prostate cancer. Patient may have had ADT

associated with salvage radiation therapy (to the primary prostate cancer or pelvis is allowed).

5.1.6 PSA ≥ 0.5 but ≤ 50 .

5.1.7 Any testosterone lab within the past 6 months $> 50\text{ng/dL}$.

5.1.8 Patient must be ≥ 18 years of age.

5.1.9 Patient must have a life expectancy ≥ 12 months.

5.1.10 Patient must have an ECOG performance status ≤ 2 .

5.1.11 Patient must have normal organ and marrow function as defined as:

Before the first administration of Xofigo, the absolute neutrophil count (ANC) should be $\geq 1.5 \times 10^9/\text{L}$, the platelet count $\geq 100 \times 10^9/\text{L}$ and hemoglobin $\geq 10 \text{ g/dL}$.

5.1.12 Patient must have the ability to understand and the willingness to sign a written informed consent document.

5.1.13 LDH lab performed within 6 months of enrollment.

5.2 Exclusion Criteria

- 5.2.1 No more than 3 years of ADT is allowed, with the most recent ADT treatment having occurred greater than 6 months prior to enrollment.
- 5.2.2 Castration-resistant prostate cancer (CRPC).
- 5.2.3 Spinal cord compression or impending spinal cord compression.
- 5.2.4 Suspected pulmonary and/or liver metastases (greater ≥ 10 mm in largest axis).
- 5.2.5 Patient receiving any other investigational agents.
- 5.2.6 Patient receiving abiraterone and prednisone.
- 5.2.7 Patient is participating in a concurrent treatment protocol.
- 5.2.8 Serum creatinine > 3 times the upper limit of normal.
- 5.2.9 Total bilirubin > 3 times the upper limit of normal.
- 5.2.10 Liver Transaminases > 5 -times the upper limit of normal.
- 5.2.11 Unable to lie flat during or tolerate PET/MRI, PET/CT or SBRT.
- 5.2.12 Prior salvage treatment to the primary prostate cancer or pelvis is allowed.
- 5.2.13 Refusal to sign informed consent.

6. PATIENT REGISTRATION AND TREATMENT PLAN

6.1 Multicenter/Participating Site Registration

Central registration for this study will take place at SKCCC, *Johns Hopkins University*.

Patient registration at each study site/institution will be conducted according to the institution's established policies. Before registration, patients will be asked to sign and date an Institutional Review Board (IRB)-approved consent form and a research authorization/HIPAA form. Patients must be registered with their local site/institution and also with the sponsor or Lead Site before beginning any treatment.

6.1.1 General Guidelines

Eligible patients will be entered on study centrally at the Sidney Kimmel Comprehensive Cancer Center at the Johns Hopkins University by the Lead Study Coordinator, [name]. All sites should call/email the coordinating

center at [contact] for registration. The Eligibility Worksheet will be supplied to each participating site.

Subjects who sign a consent form, but do not initiate protocol treatment for any reason (e.g., subjects who are screen failures), will be replaced and will not count towards our accrual goal. The Coordinating Center should be notified as soon as possible.

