6.2 Randomization

Eligibility work-up will include a complete blood count, serum chemistries, PSA, and radiographic studies (of involved sites) and bone scan (unless PET indicated). Once a signed informed consent has been obtained and after confirming patient eligibility, the lead data coordinator will assign a unique Study ID Number.

Treatment must not commence until the patient has received his identification number.

Stratification:

Subjects who meet eligibility criteria and qualify for enrollment will be stratified according to the following:

- 1) Institution
- 2) Initial treatment with surgery vs. radiation therapy
- 2) Prior hormonal therapy vs. no prior hormonal therapy
- 3) PSADT <6 months vs. 6-14.9 months

Process for Randomization:

The research team will utilize an interactive web response system (IWRS) to obtain the patient's randomization assignment. The lead coordinator will enter demographic and baseline characteristics in IWRS. The lead coordinator will obtain the patient's randomization assignment from the IWRS and appropriately notify the study site. Randomization will be 1:1 for SABR: SABR + Radium-223 arms and be stratified as above. Minimization approach will be applied to ensure balanced assignment to each treatment arm. The **ON STUDY date for protocol entry** will be the day that the study subject is randomized. Within 30 days from the date of randomization, is considered DAY 1 of SABR and/or SABR + Radium-223 Arm.

All institutions should allow 48 hours for patients to be randomized from the time they provide all eligibility documentation.

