12. DATA AND SAFETY MONITORING PLAN

12.1 Data Management

The Lead Coordinator, [name] ([contact]) will manage the study activities at each of the participating sites. The responsibilities of the Lead Coordinator include project compliance, data collection, data entry, data reporting, regulatory monitoring, problem resolution and prioritization, and coordination of the activities of the protocol team.

De-identified study data may potentially be combined with other data in future studies with the University of Maryland for other research purposes. A DUA and is in process (see Section 36 of the IRB application).

Outside participating sites will share de-identified patient data/information, with our co-investigators/sponsors (Johns Hopkins University) including genetic (somatic and germline) information that has been obtained for patient care and/or research purposes.

Eligible patients will be entered on study centrally at the Sidney Kimmel Comprehensive Cancer Center at the Johns Hopkins University by the RAVENS Lead Study Coordinator. All sites should email the the Lead Study Coordinator

([contact]). The Registration Form, and Eligibility Worksheet will be supplied to each participating site.

At the time of registration:

- Informed Consent Form (signed by the subject)
- Eligibility Checklist
- Source documents related to eligibility and randomization

The Study Coordinator at the participating site will then e-mail the RAVENS Lead Study coordinator ([contact]) to verify eligibility. To complete the registration process/randomization, the Coordinating Center will:

- Assign a patient study number
- Randomization Patient
- Register the patient on the treatment portion of the study
- E-mail the patient study number to the participating site
- E-mail the research nurse or data manager or coordinator at the participating site

If a patient does not receive protocol therapy following registration, the patient's registration on the study may be canceled. The Lead Coordinator at the Coordinating Center should be notified of cancellations as soon as possible.

Within 4 weeks after randomization:

- Baseline study case report forms
- Pertinent source documents

Within 18 weeks (4 months) after randomization:

- Day 90 study case report forms
- Xofigo 1, 2, 3 injections case report forms, if applicable
- Pertinent source documents

Within 24 weeks (6 months) after randomization:

- Day 180 study case report forms

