14.2 Sample Size/Accrual Rate/Follow-Up

The primary endpoint will be progression-free survival (PFS). Data from STOMP and ORIOLE on this patient population indicate that $\geq 50\text{-}60\%$ would show progression as defined above within a 12-month period from SABR, and a median PFS around 10 months. (72-74). We hypothesize that the addition of radium-223 will be able to reduce the risk of progression by 50%. A sample size using a 1:1 randomization scheme of 30 patients per arm will provide 80% power to detect an increase of median PFS from 10 months to 20 month (corresponding to hazard ratio 0.5) with type I error = 0.1, using one-sided log-rank test. The calculation assumes 18 months of accrual time with an additional follow-up of 12 months after the last patient is randomized. To account for 5% early drop out, we will randomize a total of 64 patients (32 per arm).

There will be no interim analysis for futility, since the progression endpoint will not have been reached by a meaningful number of patients before full accrual.

Follow-up (Every 3-6 months for 24 months or until death)

Patients will be followed for 2 years after Day One of trial or until death. Patients withdrawn from the study because of AEs will be followed until the adverse event has either resolved or stabilized. Reasons for premature withdrawal should be determined and noted.

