14.4 Analysis of Primary Objective

This is a randomized, Phase II trial of SABR *versus* SABR + Radium-223 in oligometastatic hormone sensitive prostate cancer patients. Minimization approach (77) will be applied to ensure balanced assignment to each treatment arm by stratification factors: 1) Institutional; 2)Initial treatment with surgery vs. radiation therapy; 3) Prior hormonal therapy vs. no prior hormonal therapy; and 4) PSADT <6 mos vs. 6-14.9 mos. Baseline PSA level is defined as that measured Day 1 following randomization. Progression is defined as per section 9.6.2.

The primary outcome of interest is PFS, defined as the time from the date of randomization to the date of disease progression or death, whichever happens earlier. For those who are alive and do not have progressive disease, PFS will be censored at the time of the last scan. Kaplan-Meier method will be used to summarize PFS and log-rank test will be used to compare PFS between the two arms. The analysis population includes all randomized subjects based on intent-to-treat principle.

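### Sections 6.1.1 and 12.1 permit randomized men who receive no protocol treatment to be replaced and cancelled after their arm is known, which conflicts with the all-randomized primary analysis

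*Combined protocol and SAP*

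**What the plan says.** Two administrative rules deal with men who do not start treatment.

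- Section 6.1.1: "Subjects who sign a consent form, but do not initiate protocol treatment for any reason (e.g., subjects who are screen failures), will be replaced". The sentence goes on to say that such men are not counted toward accrual. Screen failures are the only example given, but nothing confines the rule to men not yet randomized.
- Section 12.1: "If a patient does not receive protocol therapy following registration, the patient's registration on the study may be canceled". The same section introduces its list of steps with "To complete the registration process/randomization, the Coordinating Center will", and that list includes randomizing the patient. A man registered under 12.1 has therefore been randomized.

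Two statistical passages treat the same men differently.

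- Section 14.4: "The analysis population includes all randomized subjects based on intent-to-treat principle".
- Section 14.2: "To account for 5% early drop out, we will randomize a total of 64 patients (32 per arm"). The target is a number randomized, and it already allows for loss.

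On timing, section 6.2 says the on-study date "will be the day that the study subject is randomized", and it places treatment later: "Within 30 days from the date of randomization, is considered DAY 1 of SABR". Section 6.8 gives up to 60 days from randomization for SABR. The synopsis says the study is not blinded, and under section 6.2 the lead coordinator tells the site the assignment.

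**The concern.** There is a window of 30 to 60 days in which the man and his physician know the assigned arm and no treatment has been given. If he then receives nothing, the two administrative rules let him leave the count and be replaced. The reason can depend on the arm he drew. It can also depend on prognosis: section 6.11, for example, removes men found before SABR to have more than three metastases or a PSA above 50 ng/ml.

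That opens a route to exclusion after randomization in an open-label trial with 32 men per arm, where one man is 1/32, or about 3%, of an arm. At stake are who is in the primary analysis and whether the one-sided 10% error rate applies to the comparison that is delivered. Follow-up that is not collected on a cancelled man may not be recoverable at analysis.

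**Working it through.** **1. One man, followed through the text.** Take a man who is randomized and receives neither SABR nor radium-223.

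- 6.1.1: replaced, and not counted.
- 12.1: his registration may be cancelled.
- 14.2: he is one of the 64 randomized.
- 14.4: he is in the primary analysis, with PFS counted from randomization.
- 9.2: he is in neither the evaluable nor the safety population, since both require SABR.
- 9.5.5: PFS runs from the start of treatment, so he has no time origin.

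No section says that a replaced or cancelled man stays in the intention-to-treat set or is still followed. If follow-up did stop, 14.4 would censor him at his last scan. That could be the entry scan, in which case he adds nothing to the log-rank test.

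**2. The plan's own figures (14.2).** Inputs: median PFS 10 versus 20 months (hazard ratio 0.5), one-sided alpha 0.10, 80% power, 18 months of accrual plus 12 months of follow-up, 30 per arm, 5% drop-out.

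- Events needed (Schoenfeld): 4(1.282 + 0.842)² / (ln 0.5)² = 37.5, so 38.
- Event probability with exponential PFS and uniform accrual: 1 − [exp(−12λ) − exp(−30λ)] / (18λ), with λ = ln 2 / median. This gives 0.751 and 0.509.
- Expected events: 30 × (0.751 + 0.509) = 37.8.
- Power: Φ(√37.8 × 0.693/2 − 1.282) = 0.802. A log-rank simulation gives 0.800.
- Total: 60 / 0.95 = 63.2, so 64.

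The stated design reproduces.

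**3. What selective removal could do to the error rate.** The documents give no non-start rate and no prognosis for non-starters, so both are assumed here. Setting: no true effect, 10-month median, 32 per arm, one-sided test at 0.10, 50,000 simulated trials. Both arms contain k men with raised hazard. Only the radium arm's k men are removed, and typical men replace them.

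| Assumption about removed men | k = 1 | k = 2 | k = 3 |
|---|---|---|---|
| Typical of the arm | 0.101 | 0.102 | 0.104 |
| Twice the hazard | 0.114 | 0.127 | 0.141 |
| Four times the hazard | 0.119 | 0.145 | 0.169 |
| Earliest progressors in the arm (extreme bound) | 0.132 | 0.166 | 0.196 |

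With every randomized man kept, the error rate is 0.099 to 0.104 in all of these settings. A second simulation of 20,000 trials at twice the hazard gave 0.131 for k = 2 and 0.144 for k = 3. For scale, the planned 5% drop-out is 0.05 × 32 = 1.6 men per arm.

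**4. What keeping non-starters costs.** Under a true hazard ratio of 0.5 with 32 per arm, simulated power is 0.818 with no non-starters. If 1, 2 or 3 radium-arm men go untreated, carry the control hazard and are not replaced, it is 0.798, 0.783 or 0.760.

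**The case against.** The strongest case on the other side is that the sections can be read in harmony. Section 6.1.1 is triggered by consent, gives only screen failures as its example, and comes before the randomization section. Cancellation under 12.1 is discretionary. Section 6.1.1 governs counting while 14.4 governs analysis, and 14.4 is the only explicit statement of the primary analysis set. Replacing a man is compatible with intention to treat if he is still followed and analysed: simulated power with 1, 2 or 3 men both kept and replaced is 0.805, 0.791 or 0.779.

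Much of this stands. The text permits exclusion of randomized men and does not order it, so it would be too strong to say that the rules cannot all be followed. What the defence lacks is any sentence saying that a replaced or cancelled man is retained. Two sites could treat the same man differently and both be following the protocol.

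A reader might infer three stronger things that the documents do not support.

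- *Men unfit for radium drop out of one arm only.* The synopsis gives SABR to all men, and the populations in 9.2 turn on SABR. A radium-arm man who fails the blood-count check but receives SABR has arguably started protocol treatment, so neither rule removes him. The same count thresholds are an entry criterion for everyone (5.1.11). What remains specific to the radium arm is the re-check before infusion, when entry counts may be up to six months old (SBRT + Xofigo calendar, footnotes C, I and J).
- *A cancelled man has no follow-up data.* The documents are silent on follow-up after cancellation.
- *The 10% error rate is lost.* That needs removal that depends on both arm and prognosis, in the assumed direction.

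**Conclusion.** The conflict is real and concerns randomized men who receive no protocol treatment at all. Sections 6.1.1 and 12.1 together allow them to be removed and replaced once the arm is known; sections 14.2 and 14.4 count and analyse everyone randomized.

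The size is illustrative. Two to three double-hazard men removed from the radium arm only take the one-sided error from 10% to about 13–14%. Nothing happens if the men are typical of their arm. If it is poor-prognosis control-arm men who decline SABR alone and are removed, the bias runs against radium. The number of non-starters, their excess hazard and the one-sided pattern are all assumptions.

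The reason to act does not rest on those rates. It rests on an ambiguity about who is in the primary analysis, which cannot be fully repaired later if follow-up was not collected.

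**What to change.** - In 6.1.1 and 12.1, limit replacement and cancellation to men who have consented but have not been randomized.
- State that every randomized man counts toward the 64, keeps his assigned arm and is followed for PFS whether or not treatment starts.
- State that a radium-arm man who receives SABR but no radium-223 is not replaced.
- Align the PFS time origin in 9.5.5 (start of treatment) with 14.4 (randomization), so that an untreated man has a defined PFS time.

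The cost is a few sentences in an amendment and no added patients. The downside is some dilution: power is about 0.80, 0.78 or 0.76 with one, two or three untreated radium-arm men at the control hazard, against 0.82 with none. The 5% allowance was sized for loss rather than dilution, so it only partly covers retained non-starters; with two or three of them power falls below the stated 80%.
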